11.2 Disease Parameters

In order to completely document the assessment of response, the measurements of the longest tumor dimension, and its perpendicular, of all target lesions upon which the assessments of tumor response are based should be explicitly noted in the radiology report for the baseline and all subsequent follow-up exams. Reports for the follow-up exams should reiterate the measurements obtained at baseline for each target lesion. Non-target lesions or newly occurring lesions should also be enumerated in these reports, and changes in non-target lesions should be described. The same method of assessment and the same technique should be used to characterize each identified and reported lesion at baseline and during follow-up.

[figure not shown]
Tumor response criteria are determined by changes in size using the longest tumor dimension, and its perpendicular. FLAIR, T2 or post contrast T1 weighted images may be used - whichever gives the best estimate of tumor size.

Since many tumors contain non-enhancing components (or, in some cases, the tumor may not enhance at all), both the enhancing and the non-enhancing components must be evaluated – on post contrast T1 weighted images and on FLAIR/T2 weighted images respectively. Increase in enhancement on T1 weighted images without accompanying increase in disease bulk on T2 or FLAIR images is not considered tumor progression. In return, enlarging areas of non-enhancing tumor (defined as mass effect/tissue thickening) are evidence of tumor progression. Conversely, decrease in enhancing tumor component without decrease in overall FLAIR/T2 extent may represent change in tumor permeability (commonly observed with antiangiogenic therapies) rather than represent tumor response.

11.2.1 Method

The following section describes the methodology.

- For MRI imaging (preferred), the longest measurement of the tumor (or width, W) should be determined. It can be measured from the axial plane or the plane in which the tumor is best seen or measured, provided the same plane is used in follow ups. Longest diameter of target lesion(s) should be selected in the axial plane only for CT.
- The measurement (transverse (T)) perpendicular to the width in the selected plane should be determined. NOTE: A measurable lesion should have a minimal transverse measurement that is at least twice the combined thickness of the image slice and the interslice gap. For example, with a 4 mm slice and a 0.4 mm gap, minimal measurable lesion diameter is 8.8 mm. Smaller lesions would not be measurable for study purpose.
- The cystic or necrotic components of a tumor are not considered in tumor measurements. Therefore only the solid component of cystic/necrotic tumors should be measured. If cysts/necrosis composes the majority of the lesion, the lesion may not be “measurable”.
Options:
 - if the cyst/necrosis is eccentric, the W and T of the solid portion should be measured, the cyst/necrosis excluded from measurement
 - if the cyst/necrosis is central but represents a small portion of the tumor (< 25%), disregard and measure the whole lesion
 - if the cyst/necrosis is central but represents a large portion of the tumor, identify a solid aspect of the mass that can be reproducibly measured
- Leptomeningeal tumor spread is usually not a target lesion, and usually cannot be measured accurately. Presence and location of leptomeningeal tumor spread should be noted, and change in extent/thickness assessed on follow up studies.

11.2.2 Overall Response Assessment

The overall response assessment takes into account response in both target and non-target lesion, and the appearance of new lesions, where applicable, according to the criteria described in the table below. The overall response assessment is shown in the last column, and depends on the assessments of target, non-target, and new lesions in the preceding columns.

Overall Response Assessment

Target Lesions	New Lesions*	Overall Response
CR	No	CR
PR	No	PR
SD	No	SD
PD	Yes or No	PD
Any	Yes	PD
CR – Complete Response; PD – Progressive Disease; PR – Partial Response; IR – Incomplete Response; SD – Stable Disease *If CSF cytology becomes positive, it will be considered a new lesion and progressive disease.		

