11.2.3 Selection of Target and Non-target Lesions

- For most CNS tumors, only one lesion/mass is present and therefore is considered a “target” for measurement/follow up to assess for tumor progression/response.
- If multiple measurable lesions are present, a minimum of the 2 largest lesions should be measured; a maximum of 5 should be selected as “target” lesions. Target lesions should be selected on the basis of size and suitability for accurate repeated measurements. All other lesions will be followed as non-target lesions.
- The lower size limit of the target lesion(s) should be at least twice the thickness of the slices showing the tumor to decrease the partial volume effect (e.g., 8 mm lesion for a 4 mm slice).

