11.3 Tumor Response Criteria

11.3.1 Complete Response (CR)

Complete disappearance on MR of all evaluable tumor and mass effect, on a stable or decreasing dose of corticosteroids (or receiving only adrenal replacement doses), accompanied by a stable or improving neurologic examination, and maintained for at least 9 weeks. If CSF was positive, it must be negative.

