11.3.4 Progressive Disease (PD)

Progressive Disease (PD): Progressive neurologic abnormalities or worsening neurologic status not explained by causes unrelated to tumor progression (e.g., anticonvulsant or corticosteroid toxicity wean, electrolyte disturbances, sepsis, hyperglycemia, etc.), OR a greater than 25% increase in the bi-dimensional measurement, taking as a reference the smallest disease measurement recorded since the start of protocol therapy, OR the appearance of a new tumor lesion.

Increasing doses of corticosteroids required to maintain stable neurological status should be strongly considered as a sign of clinical progression unless in the context of recent wean or transient neurologic change.

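### The overall response table in section 11.2.2 leaves out the non-target input its own text relies on; read alone it conflicts with the complete response definition in 11.3.1, and some non-target progression has no explicit criterion.

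*Combined protocol and SAP*

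**What the plan says.** Section 11.2.2 states twice that non-target lesions enter the overall response. The assessment "takes into account response in both target and non-target lesion, and the appearance of new lesions, where applicable", and the result "depends on the assessments of target, non-target, and new lesions in the preceding columns". The table that follows has three columns: target lesions, new lesions and overall response. Its five rows map target CR, PR and SD without a new lesion to the same overall category, target PD to PD, and any target status with a new lesion to PD. A footnote counts CSF cytology that becomes positive as a new lesion. The legend defines "IR – Incomplete Response", a category that no row uses.

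Non-target lesions do exist under this plan. Section 11.2.3 calls for at least the two largest and at most five measurable lesions as targets, and adds: "All other lesions will be followed as non-target lesions". Section 11.2.1 says that leptomeningeal spread is usually not a target and usually cannot be measured accurately. Section 11.2 requires measurements for target lesions, while "changes in non-target lesions should be described".

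Section 11.3 defines the categories separately. CR requires "Complete disappearance on MR of all evaluable tumor and mass effect". PD requires tumor-related neurologic worsening, "a greater than 25% increase in the bi-dimensional measurement" from the smallest measurement recorded, or a new lesion.

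**The concern.** A reader classifying a scan meets two rules in the same chapter that can give different answers. The prose and 11.3.1 look at all tumor; the table looks only at the selected targets and at new lesions. Where they differ, the table gives the more favourable category.

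These categories feed the secondary objective in section 1.2.1 (response rate, duration of response and progression-free survival in DIPG patients) and the number of responses that section 13.3 plans to report for the trial. Section 9.2.2 has scans reviewed both locally and centrally. If one reader applies the table and the other applies 11.3, they can disagree on the category while agreeing on the images.

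**Working it through.** No sample size, power or error rate is involved. The check enumerates the table's logic and compares it with sections 11.2 and 11.3.

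**Assumption.** The documents define no non-target categories beyond the unused incomplete-response label. I take three levels: gone; incomplete response or stable; progressed.

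**Combinations.** Target (4: CR, PR, SD, PD) × non-target (3) × new lesion (2) = 24.

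- New lesion present: 4 × 3 = 12. All are PD, and non-target status cannot change that.
- Target PD without a new lesion: 1 × 3 = 3. All are PD.
- The rest: 24 − 12 − 3 = 9 (target CR, PR or SD, no new lesion). Here the table's answer is the same at every non-target level.

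**Where non-target status would matter.** In 4 of these 9:

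| Target | Non-target | Table gives | Sections 11.2 and 11.3 |
|---|---|---|---|
| CR | incomplete or stable | CR | 11.3.1 does not allow CR |
| CR | progressed | CR | 11.3.1 does not allow CR; PD only if 11.3.4 or 11.2 is met |
| PR | progressed | PR | PD only if 11.3.4 or 11.2 is met |
| SD | progressed | SD | PD only if 11.3.4 or 11.2 is met |

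**How far 11.2 and 11.3.4 cover the last three rows.**

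- Neurologic worsening attributable to tumor is PD, whichever lesion causes it.
- Growth above 25% is not expressly limited to target lesions, but it needs a bi-dimensional measurement, and section 11.2 requires those for targets only.
- Section 11.2 treats enlarging non-enhancing tumor as evidence of progression, again without limiting this to targets.

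What remains is a patient with enlarging non-target disease that enhances and is not measured, a stable neurologic examination and no new lesion. Leptomeningeal spread is the obvious example: section 11.2.1 asks that change in its extent be assessed but ties that to no response category.

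**Who can be affected.** Two measurable lesions should both be targets, and three to five may all be. The gap therefore concerns measurable lesions not selected, any beyond five, and lesions that cannot be measured. Section 3.1.1 excludes disseminated disease in Stratum 2 but not in Stratum 1, and 11.3.1 anticipates positive CSF.

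**The case against.** **The table may have lost a column in conversion from PDF.** The prose says "The overall response assessment is shown in the last column" and places non-target assessments in the columns before it; with the unused legend entry, that fits lost content as well as a drafting omission. But losing a column alone would leave rows that need it, such as target CR without a new lesion giving something less than CR. There are none, and all five rows are coherent with two inputs. Rows would have to be missing too. This is unlikely but not excluded; the sponsor can settle it from the source file.

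**Section 11.3 already governs.** This largely stands as a limit on the consequences. The off-treatment rule in 5.4.2 cites 11.3, not the table, and 11.3.1 is unambiguous about CR. But no sentence ranks the two. Section 11.1.1 sends the reader to the definitions below it, which include both 11.2.2 and 11.3.

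**Stronger readings the documents do not support.**

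- A reader might infer that residual non-target tumor is classed as CR under the protocol. That is true of the table only; 11.3.1 rules it out.
- A reader might infer that non-target growth can never be progression. Sections 11.2 and 11.3.4 leave the routes listed above.
- A reader might infer that every patient with more than one lesion is misclassified. Up to five lesions may be targets, and 11.2.3 says most CNS tumors present as a single lesion.
- A reader might put the effect at 1/20 = 5 percentage points per patient, from the 20 eligible Stratum 1 patients in section 2.2.2. That is not the response denominator: 11.1.1 restricts it to treated patients with measurable baseline disease who were re-evaluated, and their number is not given. A move from CR to PR would also leave the overall response rate unchanged.

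**Conclusion.** The inconsistency is real and minor. The 11.2.2 table contradicts its own text and, read alone, contradicts 11.3.1 on CR. No section gives an explicit progression criterion for enhancing or non-measurable non-target disease, and no order of precedence is stated.

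Its reach is small. It concerns patients with unselected or non-measurable lesions, chiefly in Stratum 1; few are expected in DIPG, where disseminated disease is excluded at entry. It can alter the response category, the duration of response and the progression date used for progression-free survival. Section 13.3 reports responses and progression-free survival descriptively and calls its analyses exploratory. Dose decisions rest on dose-limiting toxicities and are untouched. No percentage can be given.

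The conclusion assumes that the printed table is the sponsor's table, and the enumeration assumes three non-target levels. A consistent bias in reported efficacy would require readers to follow the table and set 11.3 aside, which nothing in the protocol tells them to do.

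**What to change.** Restore the non-target input to the 11.2.2 table, with the rows it needs, so that an overall CR requires what 11.3.1 requires. Use the incomplete-response label in the legend or delete it.

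Reconcile the table, its introductory text and 11.3.4 on how non-target change enters overall response and progression, including disease that enhances or cannot be measured, and state which section prevails if they differ. Because PD ends protocol treatment under 5.4.2, the content of any non-target progression rule is for the study committee; the request here is only that the passages agree.

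The cost is a corrected table and a sentence or two. The non-target changes already described in the radiology reports suffice, so no additional imaging or data collection is needed.

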11.2.3 Selection of Target and Non-target Lesions

- For most CNS tumors, only one lesion/mass is present and therefore is considered a “target” for measurement/follow up to assess for tumor progression/response.
- If multiple measurable lesions are present, a minimum of the 2 largest lesions should be measured; a maximum of 5 should be selected as “target” lesions. Target lesions should be selected on the basis of size and suitability for accurate repeated measurements. All other lesions will be followed as non-target lesions.
- The lower size limit of the target lesion(s) should be at least twice the thickness of the slices showing the tumor to decrease the partial volume effect (e.g., 8 mm lesion for a 4 mm slice).

11.3 Tumor Response Criteria

11.3.1 Complete Response (CR)

Complete disappearance on MR of all evaluable tumor and mass effect, on a stable or decreasing dose of corticosteroids (or receiving only adrenal replacement doses), accompanied by a stable or improving neurologic examination, and maintained for at least 9 weeks. If CSF was positive, it must be negative.

11.3.2 Partial Response (PR)

Greater than or equal to 50% reduction in tumor size by bi-dimensional measurement, as compared with the baseline measurements, on a stable or decreasing dose of corticosteroids, accompanied by a stable or improving neurologic examination, and maintained for at least 9 weeks.

11.3.3 Stable Disease (SD)

Neurologic exam is at least stable and maintenance corticosteroid dose not increased, and MR/CT imaging meets neither the criteria for PR nor the criteria for Progressive Disease.

11.3.4 Progressive Disease (PD)

Progressive Disease (PD): Progressive neurologic abnormalities or worsening neurologic status not explained by causes unrelated to tumor progression (e.g., anticonvulsant or corticosteroid toxicity wean, electrolyte disturbances, sepsis, hyperglycemia, etc.), OR a greater than 25% increase in the bi-dimensional measurement, taking as a reference the smallest disease measurement recorded since the start of protocol therapy, OR the appearance of a new tumor lesion.

Increasing doses of corticosteroids required to maintain stable neurological status should be strongly considered as a sign of clinical progression unless in the context of recent wean or transient neurologic change.

*** Consideration for possible pseudo-progression**

For patients showing possible radiographic evidence of tumor progression on MRI during the first 6 months after initiation of APX005M (on required MRI studies performed at the end of Course 2, 5, 8), the treating physician will have the option of allowing the patient to remain on study, continuing protocol therapy, and repeating disease reassessment in 4-6 weeks. Provided that the patient does not show clinical deterioration consistent with tumor progression, has been on a stable or declining dose of steroids, and the subsequent MRI demonstrates tumor regression or stable disease, then the patient will remain on study and continue protocol therapy, and the frequency of subsequent MRI will revert to pre-specified intervals. If the repeat MRI after 4-6 weeks shows disease progression, rather than pseudo-progression, then the time of progression will be the date of the initial MRI, not the follow up scan. The addition of steroids is allowed, at the time of suspected pseudo-progression, as long as the patient can be maintained on a decreasing dose.

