5.3 Concomitant Medications and Supportive Care Guidelines

5.3.1 Steroids

Corticosteroids should be used at the lowest dose to control symptoms of edema and mass effect, and discontinued, if possible. Use of corticosteroids should be recorded in the PBTC-051 database.

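### Steroids may be added before the repeat MRI that decides a suspected progression, with no reference dose, so a borderline progression can be overturned under added steroids and the PFS event delayed

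*Combined protocol and SAP*

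**What the plan says.** The pseudo-progression paragraph of section 11.3.4 covers the required MRIs at the end of courses 2, 5 and 8. If one suggests progression, the physician may continue therapy while "repeating disease reassessment in 4-6 weeks". The suspicion is set aside if the patient is not clinically worse, "has been on a stable or declining dose of steroids, and the subsequent MRI demonstrates tumor regression or stable disease". If the repeat scan shows progression, "then the time of progression will be the date of the initial MRI, not the follow up scan". The paragraph closes: "The addition of steroids is allowed, at the time of suspected pseudo-progression, as long as the patient can be maintained on a decreasing dose".

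Steroid conditions also appear elsewhere:

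- SD (11.3.3): "Neurologic exam is at least stable and maintenance corticosteroid dose not increased".
- CR and PR (11.3.1, 11.3.2): steroid dose stable or decreasing; CR also accepts adrenal replacement dosing.
- PD (11.3.4): "Increasing doses of corticosteroids required to maintain stable neurological status should be strongly considered as a sign of clinical progression", with exceptions for a recent wean or a transient neurologic change. Growth counts when the bi-dimensional product rises by more than 25%, "taking as a reference the smallest disease measurement recorded since the start of protocol therapy".

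Section 9.2 holds a second confirmation rule. Absent clinical deterioration, any initial PD is re-evaluated at the next assessment point, at least 4 weeks later. It carries no steroid condition.

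PFS is a secondary measure for DIPG patients (1.2.1), timed to PD, death or last follow-up (11.3.5) and reported descriptively (13.3). Stratum 2 expects about 12 evaluable patients (13.1.3).

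**The concern.** The repeat MRI is the test that separates pseudo-progression from progression. Allowing steroids to be added just before it means the test may be read under a treatment aimed at what is being measured. Section 5.3.1 gives the purpose of steroids: "Corticosteroids should be used at the lowest dose to control symptoms of edema and mass effect". Section 11.2 treats enlarging non-enhancing tumor, which it equates with mass effect or tissue thickening, as evidence of progression, and section 9.2 measures on T2 and/or FLAIR.

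The closing sentence asks only that the dose be falling and does not say relative to what. Two sites could classify the same patient differently: one sets the progression aside because the dose is tapering, the other lets it stand because the dose is above that at the initial scan. Where the first reading is used, the error runs one way, because a progression that is set aside leaves the PFS count at that date and can only return later. Stratum 2 has no control arm in which the same bias would appear, and a reader of the PFS curve could not tell a drug-related pseudo-progression from steroid masking.

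**Working it through.** The plan states no PFS event count, power, error rate or effect size, so there is no figure to reproduce. The check is a comparison of text plus simple arithmetic.

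**1. One patient under each rule.** Take a patient off steroids at the week-6 MRI, with growth above 25% and no clinical deterioration. Steroids are started. At the repeat MRI the dose is tapering but above zero, and the lesion is no longer more than 25% above nadir.

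| Rule | Result |
|---|---|
| 11.3.4, closing sentence | Allowed: the dose is decreasing |
| 11.3.4, stable-or-falling condition | Not met if counted from the initial MRI; met if it refers only to the time before it. The text does not say |
| 11.3.3, SD | Not met if the added course counts as maintenance dosing; otherwise met. Not defined |
| 11.3.4, PD steroid clause | Points to PD only if steroids were needed to hold neurologic status |
| 9.2 | Silent on steroids; different timing for the repeat |

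**2. Scan calendar.** Courses last 21 days, so scan week = 3 × course number. Courses 2, 5, 8 and 11 end at weeks 6, 15, 24 and 33. The repeat scan falls 4 to 6 weeks after the initial one: weeks 10–12, 19–21 or 28–30. After an overturned progression, the next scheduled MRI is 9 weeks after the initial one (15 − 6 = 24 − 15 = 33 − 24 = 9).

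**3. Shrinkage needed to fall back to the 25% limit.** The reference stays at the nadir. For a lesion a fraction x above nadir at the initial MRI, the required reduction in the product is 1 − 1.25/(1 + x):

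- x = 0.30: 1 − 1.25/1.30 = 3.8%
- x = 0.40: 1 − 1.25/1.40 = 10.7%
- x = 0.50: 1 − 1.25/1.50 = 16.7%
- x = 1.00: 1 − 1.25/2.00 = 37.5%

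Borderline cases need little change; large increases need a great deal.

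**4. Illustration on assumed inputs.** None of these inputs is in the documents: exponential progression, 12 patients, progression seen only at scheduled MRIs, and a share of progressions first seen at weeks 6, 15 or 24 overturned once and re-read at the next scheduled MRI (40,000 replicates). With a true median of 20 weeks, mean observed median PFS is 25.8 weeks with none overturned, and 26.6, 27.8 and 29.4 weeks with 10%, 25% and 50% overturned. Across true medians of 13 to 39 weeks and the same shares, the mean observed median rises by 0.2 to 4.7 weeks and 26-week PFS by 1.2 to 8.5 percentage points. Clinical progression and death between scans are ignored, so the delay at a given share is overstated.

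**The case against.** The strongest reply is that this is under-specification and not an outright contradiction. The closing sentence can be read as a conditioned exception: steroids may be added, but only with a taper. The stable-or-falling condition could refer to the period before the initial MRI, and a short tapering course need not be a maintenance dose under 11.3.3. That reading is possible, but nothing in the protocol states it, and sites must apply the text as it stands.

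The safeguards are also real. Clinical deterioration blocks the rule. Steroids needed to hold neurologic status point to PD. A repeat scan showing PD is dated back to the initial MRI. The nadir is not reset and the dose must fall, so masked growth stays open to detection later. This stands, and it confines the problem mainly to borderline radiographic cases.

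The mechanism is not quantified: no section says how far steroids change the measured area, and 11.2 also allows post-contrast T1 when it gives the best size estimate. This stands too; only the direction can be argued from the documents.

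Finally, the effect is small beside sampling error. For an exponential with a 20-week median, the approximate standard error of a 12-patient median is 20/(ln 2 × √12) = 8.3 weeks, against illustrated shifts of 0.8 to 3.6 weeks. That keeps the point in proportion, but imprecision does not remove a one-directional bias.

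**Conclusion.** The point holds in limited form. Section 11.3.4 permits steroids to be added before the deciding MRI without a reference dose, in conflict with its own condition and in tension with the SD, PR and CR definitions. A borderline radiographic progression without clinical deterioration can therefore be overturned on a scan read under added steroids, and for PFS this can only delay the event. No rule flags such a case or tests its effect on PFS.

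A reader might infer more than the documents support:

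- **That each overturned case adds at least 9 weeks.** Nine weeks is the gap to the next scheduled MRI, not a lower bound. Clinical PD or death can end PFS sooner, and section 9.2 also calls for MRI at the time of progression.
- **That each case raises 3-month PFS by 1/12 = 8.3 percentage points.** This could apply only to a week-6 progression in a patient with no clinical PD or death before 3 months. Cases at weeks 15 and 24 fall later, and no 3-month PFS endpoint is planned.
- **That true progressions are erased wholesale.** The safeguards leave mainly borderline cases exposed, and neither their number nor the steroid effect is known.

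The direction rests on the protocol's own account of what steroids are for and what is read as progression; the size rests on assumptions. PFS is secondary, descriptive and exploratory, so no error rate, power or dose decision is affected. What suffers is the interpretation of PFS and of stable-disease calls in DIPG.

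**What to change.** For endpoint classification only, with no change to treatment, steroid use, retreatment criteria (5.1.3) or off-treatment criteria (5.4.2):

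1. Reconcile sections 9.2, 11.3.3 and 11.3.4 so that they state one steroid condition, and one timing, for the scan that decides a suspected progression. The study team must choose which.
2. Record the corticosteroid dose at the initial and the repeat MRI. Section 5.3.1 already requires steroid use to be recorded; it does not say that the dose at each scan is captured.
3. Flag every progression overturned while the dose at the repeat MRI was higher than at the initial MRI.
4. Add to section 13.3 a PFS sensitivity analysis that dates progression at the initial MRI for flagged patients, reported next to the analysis as written, with the number flagged.

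A new interim status that defaults to PD is best avoided. It would touch the retreatment and off-treatment rules and could count genuine pseudo-progression as an event in the main analysis.

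The cost is a few sentences, possibly one data field, and one extra analysis in about 12 patients. The sensitivity PFS may be slightly shorter, because it may count some true pseudo-progressions as events; showing both analyses makes that visible. Stratum 2 was still accruing at this amendment, so the dose at both scans could still be collected going forward.
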